## Experimental Methods

### 1) Mini International Neuropsychiatric Interview (MINI):

The MINI was designed as a brief structured interview for the major Axis I psychiatric disorders in DSM-IV and ICD-10. Validation and reliability studies have been done comparing the MINI to the SCID-P for DSM-III-R and the CIDI (a structured interview developed by the World Health Organization). The results of these studies show that the MINI has similar reliability and validity properties, but can be administered in a much shorter period of time (mean 18.7 +/- 11.6 minutes, median 15 minutes) than the above referenced instruments. It can be used by clinicians, after a brief training session. At Visit 1, [name] or another trained interviewer will perform the interview with the subject. This interview will be more structured than usual, with very precise questions about psychological problems which require a yes or no answer by the subject.

### 2) Primary Endothelial Cell Protein Expression:

Endothelial cells will be collected from an antecubital vein, washed, isolated to slides, and stained with primary and secondary (immunofluorescence) antibodies for quantification of: ACE (Abcam), AT1 receptor (Abcam), Ang II (Novus), Aldo ([name]), nitrotyrosine (Abcam), NADPH oxidase p47phox (Abcam), Nox4 and Nox2 (Abcam). Briefly, under sterile conditions, a CRU nurse will insert an 18G catheter into an antecubital vein. [name] (with CRU nurse assisting) will insert a 0.018- or 0.021-inch mesh St. Jude 3 mm flexible guide J-wire (Daig Corp., Minnetonka, MN) 3-4 cm into catheter, then retracted 2-3 times from catheter. The distal portion of the wire is clipped off and then transferred to a 50 ml conical tube containing a buffer solution. Cells are then taken to the PIs lab (522 Fieldhouse) and cells are recovered by centrifugation, fixed to poly-lysine slides with formaldehyde, and then frozen at -80C until analysis. After blocking non-specific binding sites with 5% donkey serum (Jackson ImmunoResearch), cells will be incubated with monoclonal antibodies for proteins of interest and a specific AlexaFlour488-conjugated secondary antibody (Research Diagnostics). Slides are then cover slipped with a VECTASHIELD DAPI (4', 6' diamidino-2-phenylindol hydrochloride) fluorescent mounting medium (Vector Labs) and stored at 4C overnight. Slides are viewed using a fluorescence microscope (Eclipse 600, Nikon) and 20 individual endothelial cell images are digitally captured by a digital camera (Weiss). These endothelial cells are documented by cell staining vWF and nuclear integrity is confirmed using DAPI staining. Once endothelial cells with intact nuclei are identified, they were analyzed using Image J (NIH, Bethesda, MD) to quantify the intensity of primary antibody-dependent AlexaFlour488 staining (i.e. average pixel intensity). The number of cells typically recovered from each guide wire results in approximately 50-100 cells per slide. Eight slides and one control cultured human aortic endothelial cell (HAEC: passage 3-6 processed identically to the sample cells) slides are selected for each staining batch. Values are reported as a ratio of sample endothelial cells to HAEC average pixel fluorescence intensity to reduce variability between staining batches.

### 3) Blood Sample:

Oxidized LDL (a marker of lipoprotein oxidation 65), TNF-alpha and IL-6 will be measured by ELISA (ALPCO) by Co-I's lab. Standard blood chemistries will be determined by the hospital Pathology lab.

- 4) Venous Occlusion Plethysmography (VOP):  
Venous occlusion plethysmography (VOP) will be used to measure forearm blood flow (FBF) responses to local ischemia to test endothelium-dependent and independent dilation of forearm resistance arteries. Briefly, subjects lie supine and have blood pressure cuffs (venous occlusion) placed around upper arms and pediatric blood pressure cuffs around wrists. FBF will be measured by placing a gallium-in-silastic strain gauge around the widest part of the forearm which measures small changes in forearm volume during periodic inflation (8 sec inflated, 4 sec deflated) of upper arm cuffs to 40 mmHg (which temporarily prevents venous outflow and measures arterial inflow into forearm) and continuous wrist inflation of a blood pressure cuff to 250 mmHg. VOP is a well-established and validated technique for measuring FBF response to ischemia in human subjects.
- 5) Pulse Wave Velocity (PWV):  
Carotid-femoral, carotid-brachial, and carotid-radial PWV will be measured non-invasively by recording carotid, femoral, brachial and radial artery pressure waveforms sequentially with an applanation tonometer (Non-invasive Hemodynamics Workstation, Cardiovascular Engineering, Inc.). Pressure waveforms are gated to the ECG R wave in order to calculate the transit time (t) between the foot of the carotid and the respective peripheral (femoral, brachial, radial) waveforms. The carotid-femoral transit distance (CFTD) is estimated between the 2 anatomical sites as the difference between the suprasternal notch (SSN) to carotid (SSN-C) and femoral (SSN-F) sites. Thus, the CFTD is calculated as  $CFTD = (SSN-F) - (SSN-C)$  and PWV calculated as  $CFTD/t$  (\*CITE 1, 2). This approach accounts for parallel transmission of the pulse wave up the brachiocephalic and carotid arteries, and simultaneously along the aortic arch using the SSN as a fiducial point where parallel transmission begins (i.e. bifurcation site of aortic arch and brachiocephalic artery). The intra-subject reproducibility of carotid-femoral PWV is excellent with a coefficient variation of 2.1% for triplicate measurements on non-consecutive days in 7 young adults.
- 6) Carotid Artery Compliance (CC):  
Carotid artery compliance and Beta-stiffness index will be determined noninvasively by high-resolution ultrasonography (Logiq 7, GE Healthcare) of the right common carotid artery and contralateral assessment of carotid artery blood pressure via non-invasive carotid artery applanation tonometry respectively. Carotid artery diameters are measured ~2 cm proximal to the carotid bulb with the transducer placed at a 90° angle to the vessel by off-line analysis of DICOM images with image analysis software (Medical Imaging Applications, LLC). Maximal diameters (i.e. systolic expansion) and minimal diameters (i.e. diastolic relaxation) are measured in sync with carotid artery blood pressure waveforms. Carotid blood pressure waveforms are calibrated using diastolic and mean brachial artery blood pressure obtained from standard brachial artery cuff blood pressure.
- 7) 24-hour Ambulatory Blood Pressure Variability and Baroreflex Sensitivity:  
Twenty-four hour systolic blood pressure variability will be recorded from 24-hour blood pressure recordings using standard ambulatory blood pressure assessment (90207-IQ, Spacelabs Healthcare, Inc.). Baroreflex sensitivity will be determined by recording blood pressure and heart rate continuously for 15 minutes using beat-to-beat finger blood pressure (Finometer MIDI, Finopress Medical Systems). Blood pressure variability will be calculated

as the standard deviation of the systolic blood pressure over 24 hours, and baroreflex sensitivity will be calculated using the sequence technique as previously described.

8) Microneurography:

Direct intra-neural recordings of multiunit MSNA will be obtained from the right leg peroneal nerve using the microneurography technique as previously described. Briefly, a tungsten micro electrode (200  $\mu\text{m}$  diameter shaft; 1-5  $\mu\text{m}$  uninsulated tip) will be inserted into the peroneal nerve posterior to the head of the fibula by a physician or research staff trained in microneurography. Well-validated criteria are used to determine that a neurogram represents sympathetic activity to muscle or skin. The technique has been used safely in over 2000 studies since 1984 and it is well tolerated and reproducible. MSNA will be recorded for 30 minutes while subject is supine and quantified as burst frequency (bursts/minute) and bursts incidence (bursts/100 heartbeats). During MSNA recordings a 3-lead ECG, beat-by-beat blood pressure by finger plethysmography, and respiration will be monitored with a pneumobelt. Blood flow to the arm (brachial artery) will be measured using Doppler ultrasound to non-invasively measure mean arterial blood velocity and diameter. Two E4 wristbands (one on each wrist) will be worn by the participant to non-invasively measure sympathetic activity (electrodermal response) and beat-to-beat heart rate variability continuously. Also during the procedure subjects will undergo a mental math test and a cold pressor test. In the mental math test, the subject will be asked to subtract continuously the number 7 (or another random number) from a 3-digit number as quickly and as accurately as possible for 3 minutes. In the cold pressor test, the subject will be asked to place their hand in ice water for 2 minutes. This procedure will be used to cause transient changes in heart rate and blood pressure.

9) Retinal Vascular Measurements:

- Visual acuity will be measured by having the subject read the smallest letters on an eye chart with their glasses or best correction. This takes about 5 minutes or less.
- Intraocular pressure (IOP) may be done using a tonopen. A drop of a topical anesthetic will be placed in the eye as a numbing agent before IOP is checked. The tonopen touches the surface of the cornea of the eye very briefly. This will take a few minutes.
- Beat-by-beat blood pressure will be measured by finger plethysmography. We will have the subjects sit quietly for a few minutes. This will take a few minutes.
- Ocular Coherence Tomography (OCT): The thickness of the optic nerve and macula will also be measured inside of the eye using a special camera that forms an image of the layers of the retina. The imaging is harmless and measures the thickness or structural health of retinal layers and optic nerve. This image will be compared to the LSFG for blood vessel comparison and identification. This test takes approximately 10 minutes.
- Laser-Speckle Blood Flow Imaging (LSFG) with varying light stimuli. This device uses a Class I laser diode. Most subjects do not need dilation for this test, but those with smaller pupils may be dilated. Subjects will be seated at the instrument and we will adjust the chinrest and then let the subject rest with the lights dimmed for about 5 minutes before doing the test. Next, they will place their chin in the chinrest and look at a fixation target. This baseline test will take about 5-10 minutes. This test will be repeated following a light stimulus given to one eye using a handheld calibrated instrument in order to measure the blood flow response to activation of the retina by light. This will take another 5-10 minutes. This will be repeated several times followed by LSFG with no light stimulus at the end of testing. Two E4 wristbands (one on each wrist) will be

worn by the participant during LSFSG to non-invasively measure sympathetic activity (electrodermal response) and beat-to-beat heart rate variability continuously.

## Statistical Analysis Methods

### Descriptive Analyses

Descriptive summary statistics will be provided for demographic and important baseline characteristics. For continuous variables, the number of patients, mean, standard deviation, median, minimum and maximum will be provided. For categorical variables, the number and percent of patients in each treatment arm will be summarized.

### Primary Endpoint Analysis

Changes in our primary outcome of interest, anxiety as measured by the Beck anxiety inventory (BAI), will be assessed using a linear mixed effect model with intervention group as the fixed effect between-subjects factor of interest and repeated measurements (baseline, 6 weeks, 12 weeks) within-subjects of the anxiety inventory as the primary dependent variable. Individual participants will be initially modeled as a random effect including both an intercept term and, if necessary, slope. The random effect for slope will be removed for an intercept only model if the random slope does not substantively improve the model or if there are issues with model fitting. Fixed effects covariates for any sociodemographic or clinical variables that differ between groups despite randomization can be added.

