### Secondary Endpoint Analysis

State and Trait subscales of the STAI will be secondarily modeled as the dependent variable to assess changes in the domains of trait and state anxiety.

The novel physiological variables (vascular function, mSNA, inflammation) will serve as secondary outcomes and will be explored in analogous to the above. We will also assess for any relationship between these variables and changes in anxiety across groups in linear regression models (since these physiological variables are only measured at two points, there is no need for linear mixed models). For these latter analyses, variables for relevant sociodemographic and clinical confounds will need to be included as change in anxiety is not assigned by randomization akin to group assignment. Comparisons between the groups of higher anxiety and low anxiety will be made using one-way analysis of variance to determine differences in vascular function, mSNA, and inflammation. Baseline values for the higher anxiety group will be compared to the values obtained from the low anxiety group during their one-time experimental visit.

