## Sample Size

Using the estimating equations of Diggle et al. (2002) and based on three assessments for primary and secondary outcomes and a correlation of outcome measures over the duration of the study within individuals of 0.4, a total of 38 participants are needed per group to detect an effect size of 0.5 SD with 80% power at an  $\alpha=0.05$  (as calculated in SAS 9.3 using relevant formula). Assuming an 10% dropout rate our sample size would need to be adjusted to  $38/(1-0.1)=43$  per group using the formula from Friedman et al. (2010). A 0.5 SD difference on the anxiety inventory should represent a clinically significant effect. A corresponding change of similar magnitude on the better studied Hamilton Depression Rating Scale (not used in this study) has been considered clinically significant (Hegerl et al. 2012). Similarly, we are powered to detect clinically significant effects for the secondary outcomes of vascular function. We will

assess large vessel measures (e.g. pulse wave velocity), resistance vessel measures (forearm blood flow), and microvascular measures in the retina. In a study of brachial artery flow-mediated dilation (FMD), a reduction in FMD of 0.66 SD was associated with a 30% increased risk of cardiovascular events (Shimbo D et al. 2007). Similar results were seen in another population-based study wherein each 0.66 standard deviation in FMD was associated with an 18% increased risk of composite cardiovascular events and 36% increase risk of myocardial infarction, resuscitated cardiac arrest or coronary heart disease death (Yeboah J et al. 2009). Thus, we should be powered to detect clinically significant changes in vascular function.

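### The primary BAI model names no treatment contrast, and the 38 per group for 80% power counts the pre-treatment baseline as a visit with the full effect

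*Combined protocol and SAP*

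**What the plan says.** Primary Endpoint Analysis opens with "Changes in our primary outcome of interest, anxiety as measured by the Beck anxiety inventory (BAI), will be assessed" by a linear mixed model that has "intervention group as the fixed effect between-subjects factor of interest and repeated measurements (baseline, 6 weeks, 12 weeks) within-subjects". On the random part, "Individual participants will be initially modeled as a random effect including both an intercept term and, if necessary, slope". On adjustment, "Fixed effects covariates for any sociodemographic or clinical variables that differ between groups despite randomization can be added". The section names no fixed time effect, group-by-time term, visit or average for the comparison, and does not name baseline BAI as a covariate.

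Secondary Endpoint Analysis models the STAI subscales "to assess changes in the domains of trait and state anxiety". It says that the physiological variables "will be explored in analogous to the above", and drops mixed models for their relation to anxiety change "since these physiological variables are only measured at two points".

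Sample Size is "based on three assessments for primary and secondary outcomes", with correlation 0.4, 0.5 SD, 80% power and alpha 0.05. It gives 38 per group, or 43 with 10% dropout. Randomization is 2:1 and Description of Study Population plans 150 participants. No power is given for 150 at 2:1.

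**The concern.** Two statisticians could follow the primary analysis text faithfully and report different tests and different effect estimates. The references to change and the optional random slope point towards a group-by-time comparison. That could still be week 12 against baseline, the 6/12-week mean against baseline, or a two-degree-of-freedom interaction test.

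The sample size does not settle the matter, because it matches none of these. It credits a 0.5 SD group difference at every one of three assessments, although the BAI has only two assessments after the workshop. The stated 80% at 38 per group is therefore not what an unadjusted analysis would deliver, and whether the planned enrolment reaches 80% depends on a choice that has not been written down.

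**Working it through.** **Inputs.** From Sample Size: effect 0.5 SD, correlation 0.4, alpha 0.05, 80% power, 10% dropout. From Randomization and Description of Study Population: 2:1 and 150. Assumed: two-sided test, exchangeable correlation, SD 1 at each visit, no expected baseline difference, 0.5 SD at both weeks 6 and 12, all 150 randomised, normal approximation (t-based power is about 0.5 to 1 point lower).

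**Formulas.** For a contrast with effect Δ and per-person variance v:
- n per group = 2(1.96 + 0.842)² v/Δ²
- power = Φ(Δ/√[v(1/n₁ + 1/n₂)] − 1.96)

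**The plan's figure.** The three-visit mean has v = (1 + 2 × 0.4)/3 = 0.60. With Δ = 0.5, n = 37.7, so 38; then 38/0.9 = 42.2, so 43. Both match. One-sided testing gives 30. Other unadjusted forms with an effect only after baseline need 44 (post-treatment mean), 57 (6/12-week mean minus baseline), 63 (week 12 alone), 76 (week 12 minus baseline) or 85 (three-visit mean).

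**Variances at correlation 0.4.**
- Week 12 minus baseline: 2(1 − 0.4) = 1.20
- 6/12-week mean minus baseline: 0.70 + 1 − 0.8 = 0.90
- Week 12 alone: 1.00
- Post-treatment mean: (1 + 0.4)/2 = 0.70
- Three-visit main effect: 0.60, with Δ = (0 + 0.5 + 0.5)/3 = 0.333
- Baseline-adjusted week 12: 1 − 0.16 = 0.84
- Baseline-adjusted 6/12-week mean: 0.70 − 0.16 = 0.54

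**Example.** For the 6/12-week mean minus baseline at 38 per group, 0.5/√(0.90 × 2/38) = 2.297; less 1.96 this is 0.337, giving 63.2%. At 90:45, 1/90 + 1/45 = 1/30, so 0.5/√(0.90/30) = 2.887, giving 82.3%.

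| Contrast | 38:38 | 90:45 | 100:50 (no dropout) |
|---|---|---|---|
| Week 12 minus baseline | 51% | 70.5% | 75% |
| 6/12-week mean minus baseline | 63% | 82% | 86% |
| Group-by-visit, 2 df | 53% | 74% | 78% |
| Week 12 alone | 59% | 78% | 82% |
| Post-treatment mean, unadjusted | 74% | 90.5% | 93% |
| Three-visit main effect (0.33 SD) | 47% | 65% | 70% |
| Week 12, baseline-adjusted | 66% | 85% | 88% |
| 6/12-week mean, baseline-adjusted | 84% | 96% | 98% |

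A mixed model keeps partial data from dropouts, so actual power would lie between the last two columns.

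**Gradual effect (0.25 SD at week 6, 0.5 SD at week 12).** The adjusted average then has Δ = 0.375 and power 60%, 80% and 84% across the three columns. Adjusted week 12 is unchanged. At 90:45 the 6/12-week mean minus baseline falls to 58%, while week 12 minus baseline stays at 70.5%.

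**Correlation.** At 90:45 with a constant effect, the 6/12-week mean minus baseline has 76% power at correlation 0.3 and 94% at 0.6. The adjusted average stays at 95% or more from 0.3 to 0.7.

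**Number of assessments.** The 6-week follow-up in the Assessment Schedule includes the STAI, microneurography and venous occlusion plethysmography, but not pulse wave velocity. The count of two in Secondary Endpoint Analysis is thus wrong for sympathetic nerve activity and forearm flow. The count of three in Sample Size is wrong for outcomes such as pulse wave velocity. For a two-visit outcome at 90:45, 0.5 SD gives 70.5% (change) and 85% (adjusted). At 0.66 SD, the vascular benchmark cited in Sample Size, 0.66/√(1.20/30) = 3.30 gives 91%, and 0.66/√(0.84/30) = 3.94 gives 98%.

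**The case against.** The best defence is that the intent is readable and the enrolment generous. The primary and secondary analysis sections both speak of change, and a random slope makes sense only with time in the model. At 90:45, the 6/12-week mean minus baseline already has 82%. A baseline-adjusted average has 84% even at 38 per group. This much stands: the planned size can support a sound primary analysis, and the lowest power figures do not describe the likeliest one. It does not rescue the text, because week 12 minus baseline is an equally natural change test and has 70.5%, and baseline adjustment is not in the plan.

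A reader might infer more than the documents support:
- **That the planned test is the three-visit group main effect, understating the benefit by a third.** The text calls group the effect of interest; it does not say that group is the only fixed effect, and its references to change point elsewhere. This is the least likely intent.
- **That false positives rise to about 10%.** The figure 1 − 0.95² = 9.75% requires choosing between the main effect and the mean-change test after seeing results. The plan proposes no such choice, and each test alone keeps its 5%.
- **That 150 participants are too few.** Some contrasts fall below 80% at the planned size and others exceed it.
- **That the adjusted 6/12-week average is safely at 96%.** That holds only if the full effect is present by week 6.

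**Conclusion.** The concern holds as a mismatch between the sample size and an analysis whose treatment contrast is unspecified. The 38 per group depends on a 0.5 SD difference at a pre-treatment visit. Without it, every unadjusted contrast tried falls short of 80% at 38 per group, and power at the expected 135 completers ranges from about 65% to 90.5%. The lower end belongs to the least likely reading; the two single-contrast change tests give 70.5% and 82%.

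These figures rest on exchangeable correlation 0.4, a constant 0.5 SD effect at weeks 6 and 12, two-sided testing and randomisation of all 150. The preferred contrast depends on when the effect appears, which is a reason to name it in advance.

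**What to change.** **Primary Endpoint Analysis.** Model BAI at weeks 6 and 12 with group, categorical visit, group-by-visit and baseline BAI, or use a constrained longitudinal model with a common baseline mean. State that baseline is Visit 2, the pre-intervention visit, since the anxiety inventory is completed at both Visits 1 and 2. Name one primary contrast, week 12 or the 6/12-week average, before outcomes are examined by group. Replace covariates chosen for observed imbalance with a list fixed in advance.

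**Secondary Endpoint Analysis.** Apply the same baseline adjustment, using week 12 alone where there is no 6-week measurement. Correct the two-point statement for plethysmography and microneurography.

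**Sample Size.** Restate power for the chosen contrast with two post-treatment visits, 2:1 allocation, the number expected to be randomised and a gradual-effect sensitivity. Give the number of assessments by outcome, and show two-visit outcomes at both 0.5 and 0.66 SD.

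**Cost.** Rewording and a restated power paragraph, with no new visits or data. Adjusted week 12 needs 2.25 × 2(1.96 + 0.842)² × 0.84/0.5² = 118.7, about 119 completers; 119/0.9 = 132.2, so no added enrolment is needed for 80% if at least about 133 are randomised. Because consent comes before screening, some of the 150 may not be randomised, so that number should be stated.

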  - i) Subject will be instrumented with 24-hour ambulatory blood pressure monitor to wear home for 24 hours. Subject will return monitor to research coordinator the following day.
  - j) Subject will receive snack or meal from CRU dining room.
- 3) Visit 3: Group Intervention Workshop
- Subjects randomized to the ACT Intervention group will attend a 1-day group workshop. Each ACT group will be held at the University of Iowa Hospitals and Clinics, include a total of 8-10 subjects, and last ~4-6 hours. At the start of the workshop, participants will be asked to fill out the STAI and PANAS-X questionnaires (hard-copy). The ACT group will be conducted by either 1 or 2 psychologists. Participants will be given a booklet in which two broad areas will be covered:
- a) Behavioral Change training will involve
    - i) teaching subjects how to recognize ineffective patterns of behavior and habits
    - ii) exploring and setting life goals and those related to mental and physical health
    - iii) promoting effective and committed actions to achieve these goals despite the urge to do otherwise
  - b) Mindfulness and Acceptance Training will emphasize new ways of managing troubling thoughts, feelings, and physical sensations (i.e. learning how to recognize, and develop cognitive distances from unhelpful thoughts such as "I can't take this anymore" and learning how to willingly face experiences that cannot be changed). In-session exercises and practice will be heavily emphasized during the group intervention and handouts will be distributed for home use. Lunch will be provided and breaks will be offered to minimize fatigue.
- 4) 6-Week Post Intervention Follow-up:
- Subjects will be contacted via phone and email 6 weeks +/- 10 days after they have completed the ACT intervention group workshop.
- a) Survey Portion
- Subjects will be emailed a link to complete surveys listed below online via REDCap or have the option of completing via phone: State-Trait Anxiety Inventory; Positive and Negative Affect Schedule-Expanded Form; Anxiety Inventory; Depression Inventory; Early Experience Questionnaire; Acceptance and Action Questionnaire II; Committed Action Questionnaire; Short Form Health Survey
- b) Vascular portion of visit:
    - i) Subject will arrive at the CRU between 7-9 am after an overnight 8 hour fast (water encouraged).

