### Control Group

If randomized to the 12-week time control group, study procedures are the same as the Intervention Group with the exception of Visit 3, the Group Intervention Workshop. However, the control subjects will be emailed to complete the STAI and PANAS-X surveys prior to the ACT Group Workshop Date. The surveys will be completed online via REDCap (with individualized link as indicated).

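### ACT is delivered in workshops of 8-10, but the primary BAI model has participant random effects only, so positive within-workshop correlation would make its confidence intervals too narrow

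*Combined protocol and SAP*

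**What the plan says.** **Delivery.** Under Assessment Schedule, Intervention Group (Visit 3), each ACT workshop is to "include a total of 8-10 subjects, and last ~4-6 hours". On leaders it says: "The ACT group will be conducted by either 1 or 2 psychologists". Under Control Group, "study procedures are the same as the Intervention Group with the exception of Visit 3, the Group Intervention Workshop".

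**Analysis.** Primary Endpoint Analysis fits a linear mixed model to BAI at baseline, 6 and 12 weeks, "with intervention group as the fixed effect between-subjects factor of interest". On random effects: "Individual participants will be initially modeled as a random effect including both an intercept term and, if necessary, slope". The slope may be dropped: "The random effect for slope will be removed for an intercept only model if the random slope does not substantively improve the model". The only other option is fixed covariates for characteristics that differ between the groups. No contrast, such as group by time, is named.

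**Sample size.** The one correlation used is "a correlation of outcome measures over the duration of the study within individuals of 0.4". No section gives a workshop or therapist effect, a cluster-robust variance, an ICC, a design effect, or a sensitivity analysis for group delivery.

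**The concern.** Eight to ten people who share a day, a room and leaders may end up more alike at 6 and 12 weeks than people from different workshops. Only the ACT arm has workshops, so correlation produced by delivery can arise in that arm alone (a partially nested design). A participant intercept or slope links one person's visits to each other; it still treats different people as independent. Leaving the workshop out therefore fixes the workshop ICC at exactly zero without saying so.

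If the ICC is positive, the ACT mean is less precise than the model reports. The interval for the primary comparison is then too narrow, and the error favours finding an effect. The STAI analysis and the secondary group comparisons of change follow the same approach and share the gap; no figure is claimed for them. The comparison of higher- and low-anxiety groups uses baseline values and is not affected.

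**Working it through.** **1. The plan's own figure.** Repeated-measures formula with 3 assessments, correlation 0.4, effect 0.5 SD, two-sided alpha 0.05, 80% power:

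n = 2(1.96 + 0.84)² × (1 + 2×0.4) / (3 × 0.5²) = 37.7, so 38 per group; 38/0.9 = 42.2, so 43. Both figures reproduce. The formula contains no workshop term.

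**2. Inputs for the check.**
- From the plan: 150 enrolled, 2:1 allocation, 10% dropout, workshops of 8-10, within-person correlation 0.4.
- Derived, assuming all 150 are randomised: 100:50, so 90:45 completers, taken as 10 workshops of 9.
- Assumed: visit variance 1, and a workshop effect at 6 and 12 weeks with variance τ. The plan gives no ICC, so 0 to 0.10 is shown.

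**3. True variance of the group difference in mean post-baseline change.** Per person: (1 + 0.4)/2 + 1 − 2×0.4 = 0.9. Between groups: 0.9 × (1/90 + 1/45) = 0.030. Ten workshops add τ/10.

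**4. Variance that the random-intercept model would report.** Its residual variance is 0.6 without workshops and absorbs part of τ. A workshop pattern (0, w, w) over the three visits leaves (2/3)w² within a person. The expected extra sum of squares is (2/3) × 90 × (9/10) × τ = 54τ, on 2 × (135 − 2) = 266 degrees of freedom. The reported variance is therefore 1.5 × (0.6 + 0.203τ) / 30.

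| τ (ICC) | True variance | Reported variance | True SE / reported SE |
|---|---|---|---|
| 0 | 0.0300 | 0.0300 | 1.00 |
| 0.01 | 0.0310 | 0.0301 | 1.015 |
| 0.05 | 0.0350 | 0.0305 | 1.07 |
| 0.10 | 0.0400 | 0.0310 | 1.136 |

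The implied type I error is 2[1 − Φ(1.96/ratio)] = 5.3%, 6.7% and 8.4% at ICC 0.01, 0.05 and 0.10.

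**5. Simulation.** 40,000 null trials per cell at 90:45. Because the plan names no contrast, four tests that it permits were run. Workshop variance was either added on top, as above, or offset by scaling down individual variance so that ACT post-baseline variance stays 1. Ranges cover both conventions.

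| Test | ICC 0 | 0.01 | 0.05 | 0.10 |
|---|---|---|---|---|
| Random intercept, mean post minus baseline | 5.1% | 5.3% | 6.6-7.1% | 8.5-9.1% |
| Random intercept, 12 weeks minus baseline | 4.8% | 5.3-5.4% | 6.2-6.3% | 7.4-7.8% |
| Slope test | 4.9% | 5.3-5.4% | 6.1% | 7.2-7.4% |
| Group main effect, three visits | 4.9% | 5.2-5.3% | 6.0-6.1% | 6.9-7.1% |

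A participant random slope does not remove the inflation. At ICC 0.02 the four tests give 5.2-5.8%. The higher figures in the first row come from the scaled convention. Inverting them (1.96/1.81 and 1.96/1.69) implies SE ratios near 1.09 and 1.16, so the ratios in step 4 belong to the added-variance convention.

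**6. Other numbers randomised.** At 43:43, taken without dropout, closed form and simulation together give about 6.5-7.7% at ICC 0.05 and 8.8-10.6% at 0.10, depending on the test and workshop size.

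**7. With the workshop term.** For mean post minus baseline, the mixed model proposed under the fix, with Satterthwaite degrees of freedom, holds type I error at 4.7-5.4% over ICC 0 to 0.10. It does so even though the workshop variance is estimated at zero in 56% of trials at ICC 0 and 16% at ICC 0.05 (added variance scaled to a total of 1).

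**The case against.** **The null matters.** If the workshop changes nobody's BAI, it induces no correlation and the planned test keeps 5%. Inflation needs a zero average effect together with workshops that truly differ, some better and some worse. This stands. The more general harm is under-coverage of the interval when the ACT effect varies by workshop.

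**The size is assumed.** The intervention is one session of a few hours with a common booklet, and BAI is completed individually weeks later. The plan does not say that leaders differ between workshops; if the same people lead them all, leader differences create no between-workshop correlation. The ICC could be near zero, where the effect is negligible. This also stands.

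**The numbers randomised are uncertain.** Consent comes before eligibility screening at Visit 1, so fewer than 150 may be randomised. This stands too, but at 43:43 the inflation is larger, not smaller.

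**A shared calendar effect.** Under Control Group, "the control subjects will be emailed to complete the STAI and PANAS-X surveys prior to the ACT Group Workshop Date", so both arms may share influences of date. Such an effect largely cancels from the group contrast if controls are spread over dates as ACT participants are. In simulation it did not inflate the planned test (4.8% and 4.5% at shared variance 0.05 and 0.10). It is a separate matter from correlation caused by the workshop.

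**Stronger readings.** A reader might infer that any workshop correlation breaks the primary test. The documents do not support that: the correlation must be positive, and they give no evidence of its size. A reader might also compare the true SE with an SE calculated as if workshops did not exist, giving √(0.035/0.030) = 1.080 and √(0.040/0.030) = 1.155 at ICC 0.05 and 0.10. The planned model would not report that SE, because its residual variance takes up part of the workshop variance.

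**Conclusion.** The omission is real and conditional. The primary model has no workshop-level variance, although one arm is treated in groups of 8-10. With a positive ICC after baseline, its standard error for the group difference in change is too small. On the random-intercept mean-post-minus-baseline contrast at 90:45, with workshop variance added to a visit variance of 1, the true SE exceeds the reported one by about 1-2%, 7% and 13-14% at ICC 0.01, 0.05 and 0.10.

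Under a zero average effect with real differences between workshops, and across the four tests, type I error is about 5.2-5.4%, 6.0-7.1% and 6.9-9.1% at the same ICCs. These figures rest on an assumed ICC and on all 150 being randomised 2:1 with 10% dropout.

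A reader might go on to infer that the sample size is wrong. It is not contested: 38 and 43 follow from the stated inputs. With a partially nested design effect in the same formula, power at 90:45 is still 87-94% for ICC 0.01 to 0.10.

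This is a change that should be made because it is cheap and protects the primary interval, not because the plan shows a material error.

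**What to change.** In Primary Endpoint Analysis:
- Add a workshop random effect for the ACT arm that acts at 6 and 12 weeks only, and is zero at baseline and for controls. A workshop intercept constant over time would cancel from a change contrast and protect nothing.
- Keep the term whatever its significance, with Satterthwaite or Kenward-Roger degrees of freedom, since there will be only about 10-13 workshops.
- Keep ACT participants who attend no workshop in the ACT arm, each as a cluster of one.

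Use the same term for STAI and for the secondary group comparisons of change. Record workshop membership.

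**Cost.** If the ICC is zero, power for a 0.5 SD difference in mean post-baseline change at 90:45 falls from 82.5% to 81.5%. With the term, power on that contrast is about 75-76% at ICC 0.05 and 69-71% at 0.10; this is the price of a valid interval. If a calendar effect is shared with controls and not modelled, the test becomes conservative: type I error 3.3% at shared variance 0.05 and 2.3% at 0.10.

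**Optional, not required.** A date effect common to both arms would deal with the calendar issue. A baseline-adjusted model of the 6- and 12-week scores with an ACT-only workshop intercept would be more precise (about 89% power at ICC 0.05), but it is a different estimator and would have to be chosen in advance.
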